4 STUDY DESIGN

4.1 Overall Design

This is a randomized, single-center, open-label feasibility trial to provide preliminary signals of performance to help make decisions about whether to continue with the development of product enhancements. Four variations of the BD Nexiva PIVC (20G x 1, 20G x 1.75, 22G x 1, or 22G x 1.75) will be placed in the lower cephalic vein of both arms in approximately 40 healthy volunteers; 20 participants with 20G x 1 inch and 20G x 1.75 inch catheters, and second group of 20 participants with 22G x 1 inch and 22G x 1.75 inch catheters. PIVC indwell time will be monitored (removal at 72 hrs or upon inability to flush/aspirate) with blood collected by venipuncture (Day 1 only) and via the devices using 2 and 6mL vacutainers throughout the remainder of indwell time.

After 5 participants have completed their final visit, the in-situ catheter positions will be compared to the expected tip position based on the catheter lengths (1 inch versus 1.75 inch for either gauge). Tip position of the longer catheter is expected to reside more horizontally within the vessel. In the event catheter tip position differences are not distinct between catheter device lengths study conduct may be stopped. Additionally, this analysis will be used to refine study logistics associated with device placement, securement, sonographic measurements, and blood sample acquisition/testing over the 72-hour study duration.

Each participant will complete 6 visits: a Screening Visit (V1), followed by 4 Visits (V2-V5) to be started within 30 days after screening, and a 24-96 hour follow-up post catheter removal (V6).

The duration of the study execution is expected to be 5 months.

4.2 Scientific Rationale for Study Design

Given that participant variability (e.g., coagulation and platelet function) may impact study endpoints (e.g., device indwell time and haemolysis)²³, the current study utilizes a simultaneous paired experimental design to assess whether differences in device design (i.e., lengths of 1 inch and 1.75 inch) impact PIVC indwell time; unpaired analysis will be employed to investigate the effects of catheter gauge on PIVC indwell time. PIVC length was selected for paired analysis as it is hypothesized that longer PIVC catheters may extend indwell time based upon catheter tip location within the vessel, increased tip distance from insertion site, and reduced probability of accidental dislodgement. Although gauge is a factor that may impact indwell time, participant screening is conducted to only enroll those with catheter-to-vessel (C/V) ratios no greater than 45%; thus it is anticipated that gauge will have an effect less susceptible to participant variability and was selected for the unpaired analysis. As both device length and gauge are expected to influence haemolysis^{17,20} the study design enables evaluation of both design features.

Identification of device design factors that improve PIVC indwell time and decrease incidence of haemolysis during PIVC-based blood collection is of clinical significance due to the associated benefits for the patient (e.g., uninterrupted medical treatment, and decreased discomfort, pain and anxiety)^{28,29,33}, for the health care worker (e.g., reduced chance of needle stick injuries)²⁸, and for the healthcare institution (i.e., reduced cost of care)^{12,29}.

4.2.1 Participant Input into Design

Not applicable

4.3 End of Study Definition

A participant is considered to have completed the study if he/she has completed all required phases of the study including the last visit or the last scheduled procedure shown in the Schedule of Activities. N.B. the number of phases completed can vary depending on the longevity of the devices placed.

The end of the study is defined as the date of the last visit of the last participant in the study or last scheduled procedure shown in the Schedule of Activities for the last participant in the trial globally.

5 STUDY POPULATION

Participants of clinical trials at the Clinical Trials Unit (CTU) based at the Griffith University Gold Coast campus are recruited through two primary mechanisms: 1) local advertising via digital and paper flyers; and 2) identification of suitable participants in the CTU volunteer registry (database). All advertising in the printed and audio-visual media has prior approval of the Griffith University Human Research Ethics Committee (HREC). The CTU volunteer registry has been maintained since 2015 and currently contains more than 700 volunteers.

5.1 Inclusion Criteria

In order to be eligible to participate in this study, an individual must meet all of the following criteria:

- a. Female or Male
- b. 18-65 years of age
- c. Not pregnant at time of recruitment within 48 hrs Day 1 procedures (self-reported)
- d. Normal coagulation results (prothrombin time 13-17 sec; activated partial thromboplastin time 27-37 sec)
- e. Normal platelet aggregation results for ADP, TRAP, and collagen induced maximal amplitude (>70% amplitude over 6 mins)
- f. Target cephalic veins readily cannulatable (i.e., $\geq \sim 2.55$ mm to obtain C/V ratio less than 45% as indicated by standard 52 of the INS guidelines²⁷)
- g. Able and willing to provide verbal and written consent
- h. Current Medicare card holder

5.2 Exclusion Criteria

Participants are excluded from the study if any of the following criteria apply:

- a. History of pro coagulative state/condition (e.g. previous deep vein thrombosis)
- b. Current hypertension (e.g., systolic >139 OR diastolic >89 mmHg)
- c. Currently on any anti-coagulant or platelet inhibitor medication. Use of NSAIDs and aspirin will be documented however not exclusionary.

- d. Hemophilia or any current or history of bleeding disorder or tendency
- e. Presence or report of current blood borne disease/infection (e.g. hepatitis, HIV, leukemia, lymphoma)
- f. Difficult vascular access (i.e., vein must be readily palpable and cannulatable – no less than ~2.55 mm diameter to maintain $\leq 45\%$ C/V ratio) as indicated by standard 52 of the INS guidelines²⁷
- g. Allergy or sensitivity to chlorhexidine gluconate, isopropyl alcohol, latex, or skin adhesives
- h. BMI $< 18.5 \text{ kg/m}^2$ or $\geq 35 \text{ kg/m}^2$
- i. Positive results for the urine drug screen at screening or check-in (including opiates, methadone, cocaine, amphetamines)
- j. History or presence of alcoholism (self-reported) or drug abuse within the past 2 years
- k. A current or previous medical, physical, mental/cognitive disorders or anatomical conditions that, in the opinion of the investigator, would place the patient at risk, would make them unable to perform study procedures or has the potential to confound interpretation of the study results. (e.g., musculo-skeletal injury, chronic back pain)
- l. Employed by Becton Dickinson, Teleflex Medical, Smiths Medical or B Braun (conflict of interest)

5.3 Lifestyle Considerations

5.3.1 Lifestyle restrictions

During the participant's commitment in the study the following lifestyle restrictions will apply:

- 1) They will not be able to attend work on the days of your participation (Days 1-4 and Visits 2-5 inclusive), although limited typing, making phone calls may be possible, pending approval of the study team.
- 2) They will not be able to participate in any sport;
- 3) They will not be able to shower away from CTU (sponge bath acceptable-avoiding areas of insertion/securement dressings) while catheters are in place
- 4) They will not be able to go for a swim; and
- 5) They will not be able to undertake any physically vigorous activity.

This is so that the catheters do not dislodge from the participant's arm and so that we can minimize the chance of the participant bruising and/or getting an infection.

5.3.2 Dietary restrictions

The following items will not be consumed for the duration of the study as they impact on the participant's blood clotting capability:

- 1) beetroot³⁴;
- 2) energy drinks high in taurine content (e.g., Monster, Red Bull, Mother)³⁵; and
- 3) alcohol^{36,37}.

5.3.3 Medication restrictions

Some medications may be prohibited (e.g., ibuprofen, high-dose aspirin), while other medications are fine (e.g., magnesium): the participant will need to complete a medical history questionnaire where they indicate any medications, including over-the-counter medications, that they are currently taking to ascertain participant eligibility in the event medications may impact study results; note, if participant meets inclusion criteria and no exclusion criteria the use of current medications would not be stopped. Should a participant need to take any medications during their time participating in the study, they will be asked to please contact a member of the study team. The participant should not take any illegal drugs during involvement in the study. Similar to the dietary restrictions, these medication restrictions apply as they impact on the participant's blood clotting capability. Recreational drugs (i.e., alcohol) will also be prohibited during the period of catheterization.

5.3.4 Blood donation restrictions

The participant will not be able to donate blood during involvement in the current study. As we are already taking some of the participant's blood for the current study, the participant may feel fatigued, short-of-breath and dizzy due to losing too much blood over a short period of time if they were to also donate blood.

5.4 Screen Failures

Screen failures are defined as participants who consent to participate in the clinical study but who do not meet the inclusion criteria, or who meet the exclusion criteria. All data collected for screen failures will not be reported in the final clinical trial report.

Individuals who do not meet the criteria for participation in this study (screen failure) may not be rescreened.

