2.3.1 Risk Assessment

Anticipated risks listed below are based on known risks for study procedures to both the participant and HCP, (i.e. venipuncture, cannulation, and flush pressure monitoring). Other risks listed below for the study devices as described (listed) in the Nexiva and Diffusics IV Catheters (a-EURA).

Potential Risk of Clinical Significance	Summary of Data/Rationale for Risk	Mitigation Strategy
Study Procedures		
Venipuncture 
 • Pain • Nerve Damage • Fainting • Bleeding • Haematoma 	The risks that are associated with taking a small amount of blood are minor. A small amount of discomfort is possible during blood collection; however, this is rare, short lived and occasionally cannot even be perceived. In accordance	Infection will be minimized by using sterile needles and equipment, clean gloves, cleaning of participant skin with rubbing alcohol around the site, before collection. Bruising is a negligible risk and will be followed-up upon

Potential Risk of Clinical Significance
	
Summary of Data/Rationale for Risk
	
Mitigation Strategy

 • Infection at insertion site • Exposure to blood to either participant or HCP • Needle stick injury to either participant or HCP 	
with the collection of blood, there is a minor chance of infection at the puncture site. There is also a minor chance of developing a haematoma (bruising) at the site. There is also a possibility of fainting, light-headedness (due to nervous anxiety) after taking blood.
	
in the days after blood collection by the research team. If the participant is nervous about blood collection, they will be asked about this prior to collection so and necessary precautions taken (i.e., take blood lying down, provide water etc.). Participants will be asked to inform the team of other conditions (e.g. cold/flu, blood clotting abnormalities), so that we can minimize any risk.

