7 STUDY PROCEDURES AND ASSESSMENTS

7.1 Venipuncture-blood collection

Blood obtained via venipuncture at screening will be collected into vacutainer tubes (2mL (waste tube), 2mL BD Vacutainer® EDTA, 1.8mg/ml-1; 6 x 2.7mL BD Vacutainer® Citrate, 109 mol/m3; Becton Dickinson, USA; total volume: 20.2 mL) for assessment of inclusion and exclusion criteria (e.g., platelet aggregation, coagulation). During the study, blood will be collected from a prominent antecubital vein of the participant's non-dominant arm using a 21G needle and collection set; Becton Dickinson, USA), and a Luer-Lok™ access device and vacutainer tubes (2mL (waste tube), 2mL BD Vacutainer® EDTA, 1.8mg/ml-1; 6mL BD Vacutainer® EDTA, 1.8mg/ml-1; Becton Dickinson, USA; Total Volume: 10mL). As per Infusion Therapy Standards of Practice guidelines²⁷, the application of a tourniquet will be applied prior to venipuncture but will be limited to less than 1 minute. Once the needle has been inserted and blood has begun to flow into the waste vacutainer tube, the tourniquet will be loosened to minimize the incidence of haemolysis.

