9.4 Reporting of Events

In this study, AE collection will be limited to those occurring in the arm in which the study device is inserted, as well as any other undesirable clinical event judged to be related or possibly related to the study device, or

a study procedure regardless of anatomical region an event that, in the opinion of the investigator warrants reporting.

The Investigator must report any AEs which are serious, unanticipated/unexpected and probably or possibly related to the study product or procedures to the reviewing HREC in accordance with the relevant HREC reporting requirements.

The Investigator may also have additional responsibilities for AE reporting to their governing Health Authority which they are responsible for identifying and fulfilling.

For all adverse events collected, all sections of the appropriate Case Report Form (CRF) must be completed.

All SAEs, SADEs, and/or UADEs/USADEs must be reported to the Sponsor within one (1) working day of the site/investigator becoming aware of the event.

De-identified copies of all requested relevant documentation should be submitted to the Sponsor within 72 hours of knowledge, as appropriate.

The Sponsor will provide results of any evaluation of an unanticipated/unexpected adverse product effect to appropriate Regulatory/Health Authorities and to all Investigators within the respective reporting timelines, after the Sponsor is notified of the event. The PI will assume responsibility for submitting reports of evaluation results to their relevant HREC. The PI must notify the Sponsor in writing the report has been submitted to HREC and must retain evidence of their compliance with this requirement.

BD will comply with all other Sponsor safety reporting requirements and timelines for other entities and local health authorities in other countries where this study or other studies with the same product are being conducted, in compliance with study procedures and applicable local regulatory requirements and BD Standard Operating Procedures.

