9.5 Adverse Event (AE) Management

Collection of adverse events will begin after the participant has signed the Consent Form through the end of the participants participation in the study.

The participant will be questioned in an open-ended manner regarding any new or worsening undesirable signs or symptoms they may have experienced since starting the study. Signs and symptoms must be

comprehensively documented on the appropriate source documentation. All related signs and symptoms should be grouped under one diagnosis if possible.

Each sign, symptom, disease or illness reported must be evaluated by the Investigator or designee to determine if it meets the definition of an AE.

Any worsening or undesirable signs or symptoms of the PIVC insertion sites that results in the withdrawal of the participants from the study or, in the opinion of the Investigator or designate, warrants medical attention or medication will be considered AEs that will be subjected to the same criteria as all other AEs. Overall medical coverage for study participants will be provided by Griffith University affiliated general practitioners (GP), e.g. GPs at Griffith University Health Clinic and emergency physicians at the Gold Coast University Hospital.

If an AE or SAE occurs around the PIVC insertion site, it may be needed to take photographs of the site only. Only the Principal Investigator, Sub-investigator, study staff and Sponsor will have access to the de-identified photographs for review and assessment.

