10.3 Analysis Population

The following populations are defined as:

Population	Description
Enrolled	All participants who sign the ICF
Evaluable	All participants who complete the study until either the catheter fails or the protocol is completed (i.e., 72 hours)

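### Protocol 5.4 leaves adverse events in screen failures out of the final report, although AE collection starts at consent and screening includes a study venipuncture

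*Protocol*

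**What the plan says.** Protocol 5.4 defines screen failures as people who consent and then either miss an inclusion criterion or meet an exclusion criterion. It then states: "All data collected for screen failures will not be reported in the final clinical trial report". No category of data is exempted.

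Other sections bear on the same people:

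- **AE collection period (Protocol 9.5).** "Collection of adverse events will begin after the participant has signed the Consent Form through the end of the participants participation in the study".
- **AE scope (Protocol 9.4).** Besides events in the arm with the device, it takes in events related or possibly related to "a study procedure regardless of anatomical region". Section 9.3 counts any study-related activity as a procedure.
- **Screening draw (Protocol 7.1).** "Blood obtained via venipuncture at screening will be collected into vacutainer tubes", to a stated total of 20.2 mL, to assess eligibility.
- **Known harms (Protocol 2.3.1).** The venipuncture row lists pain, nerve damage, fainting, bleeding, haematoma, infection, blood exposure and needle stick injury. It adds: "There is also a possibility of fainting, light-headedness (due to nervous anxiety) after taking blood".
- **Populations (Protocol 10.3).** Enrolled is defined as "All participants who sign the ICF", so it includes screen failures. No safety analysis is assigned to it.
- **SAP.** Section 6.1 records how many people failed screening and is silent on their AEs. Section 7 defers all safety summaries to a safety management plan that is not among the documents.

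**The concern.** A screen failure never receives a catheter, so the harm the study can cause that person comes from the screening procedures, chiefly the blood draw. The draw is made only for the study, in a healthy volunteer with nothing to gain from it. The plan expects such events and collects them, and then rules them out of the document that gives the study's lasting account of safety. What is at stake is the completeness of the procedure-harm record in the final report. The indwell-time comparison is not touched.

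**Working it through.** There is no plan figure for the number of events affected. The check is mainly a reading of the rules in sequence, with a small amount of arithmetic.

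**Step 1. Is a harm from the screening draw a collectable AE?** Yes. Section 9.5 starts collection at consent, and screening follows consent. Section 9.3 makes the draw a procedure, and 9.4 includes procedure-related events anywhere in the body.

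**Step 2. Can a screen failure have had the draw?** Yes. The coagulation and platelet aggregation criteria in Protocol 5.1 are read from this blood, so anyone who fails on them has already been punctured. The volume in 7.1 checks: 2 (waste) + 2 (EDTA) + 6 × 2.7 (citrate) = 2 + 2 + 16.2 = 20.2 mL, as stated.

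**Step 3. Where does the event go?**

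| Destination | Governing text | Screen-failure AE included? |
|---|---|---|
| Sponsor, within 24 hours | Protocol 9.5.2, all AEs | Yes |
| Ethics committee | Protocol 9.4 | Only if serious, unexpected and probably or possibly related |
| Final clinical trial report | Protocol 5.4 | No |

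**Step 4. Does anything supplied override 5.4?** No. Protocol section 10 contains no AE analysis. SAP 4.1 defines no safety population, although SAP 6.1 points there for population membership. SAP 7 hands the matter to a plan that is not supplied. If that plan puts these AEs in the final report, it contradicts 5.4, which would still need amending.

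**Step 5. How many people could be affected?** The documents give no screen-failure rate f, so it is assumed. With 40 people passing, the number screened is 40/(1 − f), and the failures are that number minus 40:

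- f = 0.20: 40/0.80 = 50 screened, 10 failures
- f = 0.50: 40/0.50 = 80 screened, 40 failures
- f = 0.67: 40/0.33 ≈ 121 screened, about 81 failures

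These are upper bounds on unreported draws at each assumed rate. Screening also includes history, examination, a urine drug screen and vein ultrasound in no stated order, so some people may fail before any blood is taken. Extra screening for replacements under Protocol 8.3 is not counted. Without a venipuncture AE rate, people cannot be converted into events.

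**Step 6. Which way would a rate move?** Let a₁ events occur among n₁ people who pass and a₂ among n₂ punctured people who fail. Excluding failures gives a₁/n₁ in place of (a₁ + a₂)/(n₁ + n₂). The first is lower only if a₂/n₂ exceeds a₁/n₁. Nothing in the documents settles that.

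**The case against.** The strongest defence is that 5.4 limits the scope of a report and does not lose safety information. Sections 9.5 and 5.4 can both be obeyed, since one governs collection and the other reporting. The sponsor learns of every AE, the ethics committee learns of the serious, unexpected and related ones, and 9.5.1 follows ongoing events to resolution. The harms are mostly minor. All of this stands. It does not make the final report complete, and the documents give no reason for the omission.

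Stronger readings are tempting but not supported:

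- **That the rules contradict each other, or that the harms go unreported altogether.** They do not, for the reasons just given. The gap is confined to the final report.
- **That the procedure-related AE rate is biased low.** No such rate is specified in either document. Dropping screen failures also removes them from both numerator and denominator, so the direction depends on an unknown comparison.
- **That a bad reaction at screening leads to exclusion, making the omission selective.** Fainting and haematoma are not listed criteria. Only the investigator-judgement exclusion (Protocol 5.2, item k) could reach them. Someone who faints and chooses to stop is a withdrawal under 8.1, not a screen failure as 5.4 defines it. Selection is possible but not shown.
- **That every consented volunteer has the draw.** The order of screening steps is not given.
- **That the Enrolled population is disregarded for safety.** It is defined in 10.3 but never assigned a safety analysis, so no stated use is breached.

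One point of uncertainty remains. In the schedule of activities (Protocol 1.2) the AE and SAE review arrows appear to start at Day 1, which would be at odds with 9.5. The table may have been distorted when the text was extracted. The explicit wording of 9.5 is taken as governing here.

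**Conclusion.** The point holds in a limited form. A stated rule, not a missing detail, makes the final report's account of procedure harms incomplete whenever a screen failure has had an AE from a screening procedure. This rests on three things: 9.5 governs over the schedule row, 5.4 is applied as worded, and the unsupplied safety management plan does not override it. The number of events cannot be derived. The 10, 40 and about 81 people are ceilings under assumed failure rates, not estimates. The primary, secondary and exploratory endpoints are unaffected. It is worth correcting because the correction is cheap and the data will already exist, not because a distorted result has been shown.

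**What to change.** Amend Protocol 5.4 along these lines:

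> Data from screen failures will be omitted from the final report, except for the number of screen failures, the reasons for failure, and all adverse events from signature of consent.

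Then:

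1. List those AEs for the Enrolled population, and show how many people had the screening venipuncture. Use that number as the denominator for events related to the draw.
2. Refer to the same population and listing in SAP 7 and in the safety management plan.
3. Check the AE and SAE review rows of the schedule against 9.5, and reconcile them if they do start at Day 1.

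The cost is a sentence in the protocol, a cross-reference in the SAP and safety management plan, one short listing, and possibly a slightly larger AE count. SAP 6.1 already records the number failing screening. No visit, procedure or clinical rule changes.
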